Comparison of Postoperative Pulmonary Complications Between Smokers and Nonsmokers: A Prospective Cohort Study

Study Protocol and Statistical Analysis Plan

NCT Number: NCT06982911

Date: May 2025

1. Background and Rationale

Postoperative pulmonary complications (PPCs) are among the most common and clinically significant causes of morbidity and mortality following surgery. Risk factors contributing to the development of PPCs include preexisting lung disease, thoracic and upper airway surgeries, and cigarette smoking.

It is estimated that smokers have up to a sixfold increased risk of PPCs compared to nonsmokers. Previous studies suggest that smoking cessation for at least 6–8 weeks before surgery can significantly reduce the incidence of complications. Despite these findings, there remains a lack of prospective data comparing PPCs between smokers and nonsmokers undergoing elective abdominal surgery. This study aims to better characterize the impact of smoking on PPCs and guide preoperative risk assessment strategies.

2. Objective

The primary objective of this study is to compare the incidence of postoperative pulmonary complications between smokers and nonsmokers undergoing elective abdominal surgery under general anesthesia.

3. Expected Benefits

The findings of this study will clarify the risk posed by active smoking in the postoperative period, particularly for pulmonary complications. This may enhance clinical decision-making during preoperative evaluation and reinforce the importance of smoking cessation counseling.

4. Study Design and Setting

This study is designed as a prospective observational cohort study and will be conducted at Gazi Yasargil Training and Research Hospital, Diyarbakir, Turkey. Data collection is planned between February 1, 2025, and August 1, 2026.

5. Participants and Eligibility Criteria

Inclusion Criteria:

- Adults aged 18–60 years
- Undergoing elective abdominal surgery under general anesthesia
- ASA physical status I, II, III

Exclusion Criteria:

- Pregnancy
- Difficult intubation or re-intubation
- Recent upper or lower respiratory tract infection (within the last 30 days)
- Chronic pulmonary conditions (e.g., asthma, COPD, OSA)
- Emergency surgery
- Surgical duration longer than 2 hours
- Morbid obesity (BMI >35)
- Hemoglobin <10 g/dL

Patients will be categorized into two cohorts based on their smoking status:

- Smokers: ≥ 10 pack-year history
- Nonsmokers: Never smoked or quit ≥ 1 year ago

6. Sample Size Calculation

Sample size estimation was based on prior findings by Reddy et al., where the PPC rate was 54% in smokers and 16% in nonsmokers. With a power of 90% and a significance level of 5%, the required sample size was calculated to be 62 participants per group. To account for a potential 10% data loss due to dropouts or missing data, the final target sample size was adjusted to 70 participants

7. Data Collection Methods

Demographic data (age, gender, BMI), smoking status, intraoperative variables (FiO₂, PEEP, Ppeak, duration of surgery), and postoperative respiratory findings (cough, secretion, wheezing, SpO₂) will be recorded using a standardized case report form. Observations will be made at 6 and 24 hours postoperatively.

8. Outcome Measures

Primary Outcome:

- Incidence of PPCs within 24 hours postoperatively

Secondary Outcomes:

- Frequency of suctioning
- VAS score for cough severity at 6 and 24 hours

- Presence of wheezing, laryngospasm, SpO2 <90%
- Need for respiratory physiotherapy
- Length of PACU stay

9. Statistical Analysis Plan

Descriptive statistics will include means and standard deviations for continuous variables (or medians and interquartile ranges, depending on distribution) and frequencies/percentages for categorical variables.

Normality will be assessed with the Shapiro-Wilk test.

Between-group comparisons will be made using:

- Independent t-test or Mann-Whitney U test for continuous variables
- Chi-square or Fisher's exact test for categorical variables

Multivariate logistic regression analysis will be used to determine independent predictors of PPCs. Adjusted odds ratios (aORs) with 95% confidence intervals (CIs) will be reported.

Receiver Operating Characteristic (ROC) curve analysis will assess predictive performance of continuous variables like Ppeak or BMI. Area under the curve (AUC), cut-off values, sensitivity and specificity will be provided.

Sensitivity analyses will include subgroup comparisons. A post-hoc power analysis will confirm statistical adequacy based on observed effect sizes.

10. Ethical Considerations

This study was approved by the Clinical Research Ethics Committee of Gazi Yasargil Training and Research Hospital (Approval No: 257, Date: 07.02.2025). All participants will provide written informed consent.

11. Contact Information

Principal Investigator:

[name] [name]

Specialist in Anesthesiology and Reanimation
Gazi Yasargil Training and Research Hospital

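### The 10 pack-year threshold makes smokers older than nonsmokers by design, and the plan does not commit to adjusting the smoking comparison for age

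*Combined protocol and SAP*

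**What the plan says.** Section 5 sets one age range for everyone: "Adults aged 18–60 years". It then defines the exposed cohort by cumulative consumption, "Smokers: ≥ 10 pack-year history", and the comparison cohort without any dose or further age condition, "Nonsmokers: Never smoked or quit ≥ 1 year ago". A young current smoker who has not yet reached ten pack-years fits neither definition.

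Section 4 states "This study is designed as a prospective observational cohort study". No matching, stratification or balancing on age is described in any section.

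Section 7 lists "Demographic data (age, gender, BMI), smoking status, intraoperative variables" among the items on the case report form, so age will be available for every patient. In section 9, the passage that opens "Between-group comparisons will be made using" names only unadjusted tests; for a binary outcome these are chi-square or Fisher's exact. The section adds: "Multivariate logistic regression analysis will be used to determine independent predictors of PPCs". It promises adjusted odds ratios with 95% confidence intervals, but it names no covariates and does not say whether the crude or the adjusted result answers the primary objective.

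**The concern.** Pack-years accumulate with time. A minimum applied to one cohort only makes membership of that cohort depend on age: patients in their early twenties qualify freely as nonsmokers and hardly ever as smokers. The resulting age difference comes from the eligibility rules and would not shrink with a larger sample.

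If PPC risk rises with age, the young nonsmokers lower the comparison rate, and part of an age effect is reported as an effect of smoking. That error runs in the direction of the study's hypothesis. It would enter an estimate that section 1 intends for preoperative risk assessment. The unadjusted test does nothing about it, and the regression deals with it only if age happens to be among its covariates.

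**Working it through.** The plan gives no figure for age balance, so there is none to reproduce. Its planning rates (section 6: "the PPC rate was 54% in smokers and 16% in nonsmokers") give a yardstick: (0.54/0.46) / (0.16/0.84) = 6.16 as an odds ratio, and a difference of 38 percentage points.

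**Step 1: earliest age at which a patient can be a smoker.** Formula: starting age + 10 / (packs per day). The threshold is from section 5; starting age and daily amount are assumptions.

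- One pack a day from 15: 15 + 10/1 = 25
- One pack a day from 18: 18 + 10/1 = 28
- Two packs a day from 15 or 18: 15 + 10/2 = 20, or 18 + 10/2 = 23
- Half a pack a day from 15 or 18: 15 + 10/0.5 = 35, or 18 + 10/0.5 = 38
- To qualify at 18 after starting at 12: 10/6 = 1.67 packs a day

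**Step 2: share of the age range with practically only nonsmokers.** Formula: (earliest age − 18) / 42.

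- Edge at 25: 7/42 = 17%, leaving 83% shared
- Edge at 28: 10/42 = 24%, leaving 76% shared

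**Step 3: age gap.** With ages uniform in each cohort (assumed), the mean is (18 + 60)/2 = 39 for nonsmokers, and (25 + 60)/2 = 42.5 or (28 + 60)/2 = 44 for smokers. The gap is 3.5 or 5.0 years.

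**Step 4: crude odds ratio produced by age alone.** Suppose smoking has no effect. Let logit p(age) = a + (ln R / 10)(age − 39), where R is the odds multiplier per decade. Choose a so that the average risk over nonsmoker ages is 16%. Average the same curve over ages from the edge to 60 to get the smoker rate. The odds ratio is then [p/(1 − p)] / (0.16/0.84). R from 1.25 to 2.0 is an assumption; the documents give no age slope.

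| Age distribution (assumed) | Edge | Smoker rate, R = 1.25 | Smoker rate, R = 2.0 | Crude OR |
|---|---|---|---|---|
| Uniform | 25 | 16.96% | 18.33% | 1.07–1.18 |
| Uniform | 28 | 17.40% | 19.49% | 1.11–1.27 |
| Bell-shaped, mean 42, SD 11, cut to 18–60 | 25 | 16.27% | 16.61% | 1.02–1.05 |
| Bell-shaped, mean 42, SD 11, cut to 18–60 | 28 | 16.47% | 17.13% | 1.04–1.09 |

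In the bell-shaped case only about 5% of nonsmokers are below 25 and 9% below 28, which is why the effect shrinks.

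The model gives smokers above the edge the same age pattern as nonsmokers above it. That probably understates the gap, because smokers just above the edge must have started earliest or smoked most.

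**The case against.** The strongest reply is that a minimum-exposure threshold is a legitimate design choice, that any pack-year definition correlates with age, and that the plan already has the tools: age is recorded and a multivariable model is planned. Section 1 does not list age among the risk factors for PPCs, so the slope is brought in from outside. Even the largest distortion in the table is small beside an odds ratio of about 6.2.

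Much of this stands. The slope and the age distributions are assumptions, and a bias of this size could not produce the planned difference. An age term would also deal with most of the problem, since the smoking coefficient would be estimated mainly from the wide range of ages found in both cohorts. What does not stand is that the plan already secures this. Recording age does not commit the analysis to using it, and a model described as a search for independent predictors need not retain it.

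Two stronger readings are tempting, and the documents support neither.

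- A reader might infer that the cohorts share no age range, or that the youngest ages can hold only nonsmokers. Both cohorts are eligible from 18 to 60, very early or heavy smokers can qualify in their early twenties or before, and at one pack a day the overlap covers 76–83% of the range.
- A reader might take the half-pack case as an upper bound: an edge at 35–38, 40–48% of the range without smokers, and a crude odds ratio of 1.23–1.67 (uniform ages, edge at 38). That requires every smoker to smoke half a pack a day. In a mixed population the heavier and earlier smokers set the edge.

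**Conclusion.** The point holds as a modest, correctable bias. Followed as written, the plan links age to exposure through the cohort definitions, tests the difference without adjustment, and leaves age adjustment to later choice. Patients below about 25–28 will be almost all nonsmokers, and the direction of the bias favours the hypothesis if PPC risk rises with age.

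Under the stated assumptions (no true smoking effect, 16% nonsmoker risk, odds rising 1.25- to 2.0-fold per decade), the crude odds ratio from age alone is about 1.07–1.27 with uniform ages and about 1.02–1.09 with ages clustered around 42. If risk does not vary with age between 18 and 60, there is no bias. The figures do not suggest that the smoking comparison as a whole is invalid. They show that the reported size of the effect could be somewhat inflated, and that the data needed to prevent this are already being collected.

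**What to change.** Add to section 9 that the primary smoker–nonsmoker estimate is the age-adjusted odds ratio for PPC with its 95% confidence interval, from a logistic model containing smoking status and age as a continuous covariate. Compute it in patients at or above a lower age limit. Fix that limit before outcomes are analysed, from the ages of the enrolled smokers, at the age where smokers are actually represented; one unusually young heavy smoker should not set it. Report the unrestricted crude comparison as secondary.

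Adjustment should lead, because restriction alone leaves confounding inside the overlap, where cumulative dose still rises with age. The limit then keeps the model from extrapolating to ages without smokers. A higher age bound at enrolment or frequency matching by age would change recruitment after its planned start in February 2025, and is not needed to deal with a bias of this size.

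The cost is a short addition to the SAP, with no new data and no change to recruitment. A few young nonsmokers leave the primary comparison, and precision falls slightly.

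### Section 6 states 62 per group for 90% power, but its own inputs need about 31 per group, and the final target of 70 has no unit

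*Combined protocol and SAP*

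**What the plan says.** Section 6 (Sample Size Calculation) takes its rates from a cited prior study: "the PPC rate was 54% in smokers and 16% in nonsmokers". It continues: "With a power of 90% and a significance level of 5%, the required sample size was calculated to be 62 participants per group". The allowance for loss follows: "To account for a potential 10% data loss due to dropouts or missing data", "the final target sample size was adjusted to 70 participants". The last sentence does not say whether 70 is a total or a per-group number, and no total sample size appears elsewhere in the document.

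Section 6 does not name the test, the sidedness or the allocation ratio behind the calculation. Equal groups are implied by the single per-group figure. Section 9 gives the comparison for binary outcomes as "Chi-square or Fisher's exact test for categorical variables" and adds: "Multivariate logistic regression analysis will be used to determine independent predictors of PPCs". It also plans ROC and subgroup analyses.

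**The concern.** A difference of 38 percentage points (54% against 16%) is large, and 62 per group is far more than 90% power at the 5% level normally requires for it. The stated size and the stated power therefore cannot both be right for the stated rates.

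The target of 70 adds a second problem. As a total, it is smaller than the 2 x 62 = 124 that the preceding sentence implies before any loss. As a per-group number, it is a sensible inflation of 62 but inherits the mismatch with 90% power. At stake are the enrolment target (70 or 140 people), the stated justification for it, and the number of PPC events available for the Section 9 analyses.

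**Working it through.** **Inputs (Section 6).** p1 = 0.54, p2 = 0.16, difference 0.38, mean rate 0.35, power 90% (z = 1.2816), significance level 5%, loss 10%. Assumed because not stated: two-sided (z = 1.96) and 1:1 groups. One-sided variants (z = 1.645) were also tried.

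**Step 1. Try to reproduce 62 per group.** Pooled chi-square formula:

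n = [1.96 x sqrt(2 x 0.35 x 0.65) + 1.2816 x sqrt(0.54 x 0.46 + 0.16 x 0.84)]² / 0.38² = 30.98, so 31 per group.

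Continuity correction: (30.98/4) x [1 + sqrt(1 + 4/(30.98 x 0.38))]² = 36.05, so 37 per group.

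Unpooled variance: (1.96 + 1.2816)² x (0.2484 + 0.1344) / 0.38² = 27.85, so 28 per group.

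| Method, 90% power, 1:1 | Two-sided 5%, per group | One-sided 5%, per group |
|---|---|---|
| Pooled chi-square | 31 (30.98) | 26 (25.06) |
| Arcsine | 31 (30.66) | 25 (24.99) |
| Unpooled | 28 (27.85) | 23 (22.70) |
| Continuity-corrected | 37 (36.05) | 31 (30.10) |
| Fisher's exact, by enumeration | 35 (power 90.04%; 34 gives 89.0%) | not run |

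None gives 62. Even 99% power, two-sided, needs only 53 per group (58 with continuity correction). Unequal allocation does not help: a 3:1 split gives 62 in the larger group but about 21 in the other, which is not 62 in each.

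**Step 2. Power at 62 per group.** [0.38 x sqrt(62) − 1.96 x sqrt(0.455)] / sqrt(0.3828) = 2.70, so power is 99.65%. Exact enumeration gives 99.6% for chi-square and 99.4% for Fisher. At 31 per group the same approximation gives 90.0%.

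**Step 3. What 62 does match.** 2 x 31 = 62, the total from the pooled two-sided formula.

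**Step 4. The target of 70.**
- If 62 is a total: 31/0.9 = 34.4, so 35 per group and 70 in total.
- If 62 is per group: 62/0.9 = 68.9, so 69, rounded up to 70 per group and 140 in total. The total before rounding up is 124/0.9 = 137.8, about 138.

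Both fit, so the arithmetic does not settle the unit.

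**Step 5. What each reading delivers after 10% loss.** Expected events = n per group x (0.54 + 0.16).

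| Reading of 70 | Evaluable per group | Power, chi-square | Power, Fisher | Expected PPC events |
|---|---|---|---|---|
| In total | about 31 | 90.0% | 85.1% | 31 x 0.70 = 21.7 |
| Per group | 63 | 99.7% | 99.4% | 63 x 0.70 = 44.1 |

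**The case against.** The best defence concerns the 70. In the text as read from the PDF, that sentence ends without a full stop, so a unit may have been lost in extraction. Read straight on from 62 per group, an upward adjustment to 70 also points to per group, since an allowance for loss cannot shrink 124 to 70. Both points are fair, and the missing unit is less certain than the power mismatch. They do not rescue Section 6: if the lost words were per group, the size still contradicts 90% power; if they were in total, 70 contradicts 62 per group.

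A second objection is that the harm is small. This stands in part. The study is observational, so extra participants are exposed to no assigned treatment, and neither reading seriously weakens the unadjusted comparison. The 85.1% for Fisher's test should not be pressed either: at 31 per group the smallest expected cell is about 31 x 0.35 = 10.9, so the usual small-count reason for that test would not arise at the assumed rates.

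Third, Section 9 lists no covariates, so the document cannot show whether 22 or 44 events are enough for the model. That is correct. The event counts show only that the two readings differ twofold.

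**Conclusion.** The concern holds. From Section 6's own rates, power and significance level, 62 per group is about twice what is needed: 31 by the pooled two-sided chi-square formula, and 23 to 37 across the 1:1 methods tried. Its power is about 99.7%, against the 90% stated. This does not depend on sidedness, on the choice between chi-square and Fisher, or on how 70 is read. It assumes equal groups, which the single per-group figure implies.

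That a total was mislabelled is the likeliest explanation, but it is an inference. As the text stands, the unit of 70 is not stated, and the document supports an enrolment of either 70 or 140. The consequence is an unclear target and a misstated justification, not an underpowered primary comparison.

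**What to change.** The sponsor should confirm whether 62 and 70 are totals or per-group numbers, name the test and sidedness used for the calculation, and replace the Section 6 figures with one of the following.

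- **If totals:** 31 per group (62 in total) give 90% power by two-sided chi-square test at the 5% level for 54% against 16%; allowing for 10% loss, 35 per group (70 in total).
- **If per group:** 62 evaluable per group give about 99.7% power by the same test for 54% against 16%; allowing for 10% loss, 70 per group (140 in total). The sponsor may add that 62 per group give 90% power for about 42% against 16% by chi-square (between 43% and 44% against 16% by Fisher). The 42% has no source in the document, so it would need its own justification.

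If Fisher's exact test is named instead, 35 evaluable per group are needed, and 35/0.9 = 38.9 gives 39 per group (78 in total), so 70 in total would fall short of 90%.

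In choosing, the sponsor should weigh the expected events, about 22 or 44, against the logistic regression planned in Section 9. The post-hoc power analysis planned there cannot make up for an unclear target.

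The cost is a wording correction if the site already recruits to the confirmed number. If it is recruiting to 70 in total and 140 was meant, the cost is 140 − 70 = 70 more participants. Section 4 plans data collection to August 1, 2026, so this should be settled before recruitment closes.

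### No preoperative reading of cough, secretions or wheeze is stated, so the cough VAS and wheeze comparisons can mix pre-existing with new symptoms

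*Combined protocol and SAP*

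**What the plan says.** **Section 7 (Data Collection Methods)** lists age, gender, BMI, smoking status and intraoperative variables, and then "postoperative respiratory findings (cough, secretion, wheezing, SpO₂) will be recorded using a standardized case report form". The only times given are these: "Observations will be made at 6 and 24 hours postoperatively".

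**Section 8 (Outcome Measures)** gives the primary outcome as "Incidence of PPCs within 24 hours postoperatively", without defining a PPC. The secondary outcomes include "VAS score for cough severity at 6 and 24 hours" and "Presence of wheezing, laryngospasm, SpO2 <90" percent. The first is a score rather than a change, and the second is presence rather than new onset.

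**Section 9 (Statistical Analysis Plan)** compares the cohorts with a t-test or Mann-Whitney test and a chi-square or Fisher test. The one adjusted model is a logistic regression for PPCs, and its covariates are not named. On sensitivity analyses it says only: "Sensitivity analyses will include subgroup comparisons".

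**Section 5 (Participants and Eligibility Criteria)** excludes chronic pulmonary conditions and respiratory infection in the last 30 days. Smokers are those with at least 10 pack-years. Nonsmokers have never smoked or stopped at least a year ago.

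**The concern.** A smoker without a diagnosed lung disease or a recent infection can still have a habitual cough or sputum. Measured only after surgery, that symptom looks the same as one that surgery and anaesthesia provoked. The exposure is itself plausibly linked to the prior symptom, so the contamination would be differential and would tend to widen the smoker-nonsmoker gap.

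At stake is what the cough and wheeze results mean. A difference could be read as a postoperative effect when part of it was there before induction. Adjusting for the variables listed in Section 7 cannot separate the two, because the preoperative respiratory state is not among them. A baseline that is never recorded also cannot be recovered at analysis.

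**Working it through.** **1. What is and is not stated.** The symptoms are labelled postoperative (Section 7), timed at 6 and 24 hours (Section 7), scored as absolute level or presence (Section 8) and tested without adjustment (Section 9). No section gives a preoperative value, a change score or a new-onset rule. The form is not shown, so the finding is that a baseline is not stated, not that it is not collected.

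**2. Possible size (every input is assumed).** Let r be the new-onset risk, equal in both cohorts, a the prevalence before surgery, and c the share of prior symptoms still present and counted. With prior and new symptoms independent:

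apparent rate = 1 − (1 − c·a)(1 − r)

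spurious difference = c(1 − r)(a_smokers − a_nonsmokers)

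For wheeze, take r = 10%, a_nonsmokers = 5% and c = 1. The nonsmoker rate is 1 − 0.95 × 0.90 = 14.5%.

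| Smoker prevalence before surgery | Apparent smoker rate | Spurious difference | Chance of p < 0.05, 62 per group |
|---|---|---|---|
| 5% | 14.5% | 0 | nominal level |
| 10% | 19.0% | 4.5 points | about 10% |
| 20% | 28.0% | 13.5 points | about 45% |
| 30% | 37.0% | 22.5 points | about 83% |

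The last column uses the two-sided normal approximation. If half of the prior symptoms are counted (c = 0.5), the differences halve to about 2.3, 6.8 and 11.3 points. For the cough VAS, a pre-existing shift of 0.2, 0.35 or 0.5 SD gives a significant result with probability about 20%, 50% or 80% at 62 per group, with no true difference in new cough.

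**3. Which sample size applies.** The cost of a late change depends on the evaluable number. Section 6 gives 54% vs 16%, 90% power, 5% significance and 62 per group, then a target of 70 not labelled as per group or total. The two-sided pooled formula, with mean rate 0.35, gives:

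n = [1.960·√(2 × 0.35 × 0.65) + 1.282·√(0.54 × 0.46 + 0.16 × 0.84)]² / 0.38² = 4.473 / 0.1444 = 30.98, so 31 per group

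The stated 62 matches the total, 2 × 31, and 62/0.9 = 69 is close to 70. Both evaluable bases are therefore carried forward: 62 per group as written, and 31 per group if 70 is a total.

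**4. Patients without a baseline.** Section 4 says: "Data collection is planned between February 1, 2025, and August 1, 2026". That is 546 days. With even accrual:

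- Change on 1 May 2025: 89/546 = 16.3% have no baseline.
- Change on 31 May 2025: 119/546 = 21.8%.
- Change on 1 November 2025: 273/546 = 50.0%.

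For a May 2025 change the evaluable numbers with a baseline are 62 × (0.782 to 0.837) = 48.5 to 51.9 per group, or 31 × the same = 24.2 to 25.9.

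**5. Power of a new-or-worse PPC analysis,** by exact binomial enumeration with the uncorrected chi-square test, two-sided 5%, at 54% vs 16%: 98-99% with 48-52 per group, and about 82-86% with 24-26. A change on 1 November 2025 leaves 31 of 62 (about 90%), or 15-16 of 31 (about 62-66%).

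**6. If new-only rates are lower.** Suppose the planned rates already counted all prior symptoms, at assumed prevalences of 10-30% in smokers and 2-5% in nonsmokers. Then the new-only rate is 1 − (1 − p)/(1 − a). Smokers: 1 − 0.46/0.90 = 49% down to 1 − 0.46/0.70 = 34%. Nonsmokers: 1 − 0.84/0.98 = 14% down to 1 − 0.84/0.95 = 12%. Power is then 64-99% with 48-52 per group, and about 38-88% with 24-26.

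**The case against.** The strongest reply has four parts.

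- **The form may already hold a baseline.** Section 7 is a one-sentence summary of a form that the reader cannot see. This stands as a limit. If the baseline is there, the data-collection half of the remedy reduces to saying so. The analysis half remains, because Sections 8 and 9 use no baseline.
- **The exclusions deal with it.** Section 5 removes diagnosed lung disease and recent infection, which plausibly bears more on wheeze than on cough. This lowers the risk, but Section 5 names no symptom screen.
- **Total symptom burden is a legitimate target.** The aims in Sections 1 and 3 concern the impact and risk of smoking, and habitual cough may be part of that. This stands, and is why the as-worded analysis should remain and any baseline adjustment should be supplementary.
- **The outcomes do not contradict their own wording.** A reader might infer that they do, because Section 2 sets out to "compare the incidence of postoperative pulmonary complications between smokers and nonsmokers". But incidence is used there, and in Section 8, only for PPCs. The cough and wheeze outcomes are worded as a score and as presence, so there is no internal contradiction.

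A reader might also infer that the primary result is biased. The documents do not support that: PPC is undefined, and the primary outcome is exposed only if cough, secretion or wheeze counts towards it.

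**Conclusion.** The point holds as a cheap improvement. As written, the plan gives no means of separating new from pre-existing cough or wheeze, and the firm reach is the cough VAS and wheeze secondary outcomes. The direction, towards exaggerating the smoking difference, rests on prior symptoms being more common in smokers. With equal prevalence there is no bias. No bias is claimed for SpO2 below 90%.

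The documents give no size. The 4.5 to 22.5 points shown for wheeze depend wholly on assumed prevalences and on all prior wheeze being counted, so they show what is possible and do not estimate what will occur. It would also be too strong to say that the trial fails to collect a baseline; the documents show only that none is stated.

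**What to change.** 1. Add preoperative cough VAS, secretion and wheeze to the existing form, or state that it already holds them.
2. Report these findings, and any symptom component of PPC, as new or worse than the preoperative reading, alongside the as-worded result. All patients stay in the as-worded analysis.
3. Present a baseline-adjusted cough VAS comparison as supplementary only, because baseline cough may itself be an effect of smoking.
4. State how many patients in each cohort have no baseline and so cannot enter the new-or-worse analysis.

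The cost is a few form fields and a wording amendment. The real downside is the loss of patients enrolled before the change. May 2025 is the month in which the document is dated, so the 16-22% loss is close to a best case, and it grows with delay. Because a later change or lower new-only rates reduce power, the new-or-worse result should supplement the as-worded analysis and not replace it.

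### ROC cut-offs have no pre-set value, selection rule or internal correction, so their sensitivity and specificity will on average be optimistic

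*Combined protocol and SAP*

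**What the plan says.** Section 9 of the combined protocol and SAP says that ROC analysis "will assess predictive performance of continuous variables like Ppeak or BMI", and then: "Area under the curve (AUC), cut-off values, sensitivity and specificity will be provided". The list of predictors is open-ended. The section gives no cut-off value, no rule for choosing one, and no statement of whether high or low values indicate risk. It describes no split sample, cross-validation, bootstrap or external cohort. Confidence intervals are promised for the adjusted odds ratios but not for the ROC results. The only sensitivity analyses named are subgroup comparisons.

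Section 4 describes one cohort at one hospital. On its size, Section 6 says "the required sample size was calculated to be 62 participants per group" and, after an allowance for 10% loss, "the final target sample size was adjusted to 70 participants". It does not say whether 70 is per group or the total.

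**The concern.** If a threshold is chosen because it separates these patients best, and its sensitivity and specificity are then computed in the same patients, part of the apparent separation is chance that the search has picked out. New patients will not reproduce that part. The plan describes the result as predictive performance, which is a claim about patients outside the sample, yet it has no step that estimates performance outside the sample.

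With few events the inflation is not negligible and the threshold itself is unstable. Sections 1 and 3 say the study is meant to inform preoperative risk assessment, so a published BMI cut-off in particular could be taken as more accurate than it is.

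**Working it through.** **The plan's own figures.** The documents give no ROC figure to reproduce. The nearest is the sample size, which matters here because it sets the number of events. Section 6 assumes that "the PPC rate was 54% in smokers and 16% in nonsmokers", with 90% power and 5% significance (taken as two-sided; sidedness is not stated).

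- Formula: n per group = [1.960·√(2·p̄·(1−p̄)) + 1.282·√(p₁(1−p₁) + p₂(1−p₂))]² / (p₁−p₂)²
- p̄ = (0.54 + 0.16)/2 = 0.35, so √(2·0.35·0.65) = 0.6745
- √(0.54·0.46 + 0.16·0.84) = √0.3828 = 0.6187
- n = (1.322 + 0.793)² / 0.38² = 4.473/0.1444 = 31.0, so 31 per group and 62 in total

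The stated 62 therefore matches a total, not a per-group requirement, and 62/0.9 = 68.9, close to 70. Read in sequence, however, the text suggests 70 per group. That is a separate matter, so both sizes are carried forward.

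**Events, equal groups assumed.** 70 × 0.35 = 24.5, about 25. 140 × 0.35 = 49.

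**Simulation.** One normally distributed predictor with equal variance in patients with and without a complication. The mean difference is d = √2·Φ⁻¹(AUC) standard deviations. The cut-off is the value that maximises J = sensitivity + specificity − 1 (Youden). Apparent J is J at that cut-off in the same data. Achieved J is what the same cut-off would give in new patients. There were 3,000 to 6,000 simulated cohorts per scenario. The plan specifies neither the Youden rule, nor normality, nor the true AUCs, so these are assumptions.

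| Scenario (35% complication rate) | N = 70: apparent / achieved J | N = 140: apparent / achieved J |
|---|---|---|
| AUC 0.50, direction fixed | 0.15 / 0 | 0.10 / 0 |
| AUC 0.50, direction picked from the data | 0.20 / 0 | 0.15 / 0 |
| AUC 0.65, direction fixed | 0.32 / 0.19 | 0.28 / 0.20 |
| AUC 0.70, direction fixed | 0.39 / 0.27 | 0.35 / 0.27 |
| AUC 0.80, direction fixed | 0.53 / 0.42 | 0.50 / 0.43 |

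- For the useless predictor with direction fixed, mean apparent sensitivity/specificity is 60%/54% at N = 70 and 58%/53% at N = 140. The 95th percentile of apparent J is 0.29 and 0.21.
- Mean AUC in those runs is 0.50, so the AUC itself is not inflated when the direction is fixed.
- If only 10% of patients had a complication, the useless predictor's apparent J would be 0.23 (N = 70) or 0.17 (N = 140), direction fixed.
- At N = 1,000 and AUC 0.6 to 0.8, the excess falls to 0.02–0.03, which shows that it is a small-sample effect.
- At AUC 0.65, the middle 80% of chosen cut-offs spans about 1.3 standard deviations of the predictor at N = 70 and about 1.1 at N = 140.

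**Do the remedies work?** For the useless predictor (true J = 0), 10-fold cross-validation with the cut-off re-selected in every fold gives a mean J between −0.01 and 0.01 at both sizes. Bootstrap optimism correction leaves about 0.05–0.06 at N = 70 and 0.03–0.04 at N = 140. At AUC 0.65, cross-validation gives 0.18 and 0.20, and the bootstrap 0.23 and 0.23, against 0.19 and 0.20 achieved.

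**The case against.** The strongest reply is that this is a supplementary analysis. ROC work appears neither in the objective (Section 2) nor among the outcomes (Section 8), and the smoker/nonsmoker comparison does not depend on it. That stands, and it limits the priority of the point. It does not remove the bias, and Section 9 does not label the ROC results exploratory.

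A second reply is that the plan never says cut-offs will be picked from the data. That is true: it is an inference. It rests on cut-offs being listed as outputs, with none given beforehand and no other data source described.

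Several stronger readings are tempting but unsupported:

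- A reader might take 0.20 (N = 70) or 0.15 (N = 140) as the size of the bias. Those figures also need the direction to be chosen from the data. The plan is silent on direction, and higher-is-worse is the natural prior for both named variables.
- A reader might infer that a worthless variable would be published with a useful-looking threshold. Averages of about 60%/54% or 58%/53% would persuade few people, and the AUC reported alongside would average 0.50. It could happen in a given study, but it is not the expected result.
- A reader might see both cut-offs as preoperative thresholds. Section 7 lists Ppeak as an intraoperative variable. Only BMI could serve before surgery, and its range is cut by the exclusion above 35. Nothing in the documents says a cut-off will direct care.

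**Conclusion.** The point holds as a moderate, average bias in a supplementary analysis. Followed as written, Section 9 would report sensitivity and specificity whose sum is on average too high. With direction fixed, the excess for a useless predictor is about 0.15 on J if 70 is the total and about 0.10 if it is per group. For a predictor with true AUC 0.65 it is about 0.13 (0.32 − 0.19) or 0.08 (0.28 − 0.20).

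The size depends on the assumed Youden rule, a normal predictor and the planning complication rates. It grows with fewer events, with a data-chosen direction, or if the best of several predictors is reported. A single study can fall below these averages. The direction of the bias does not depend on how the target of 70 is read. The sponsor should correct this before analysis, but it does not threaten the primary result.

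**What to change.** Amend Section 9 to:

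1. Name the predictors for ROC analysis, the direction of each, and one cut-off rule (for example Youden).
2. Report each AUC with a 95% CI.
3. Report sensitivity and specificity from cross-validation that repeats the cut-off selection in each fold (for example repeated 10-fold). Bootstrap optimism correction is an alternative, provided the report notes that it leaves some bias, roughly 0.03–0.06 on J for a useless predictor at these sample sizes.
4. Give a bootstrap interval for each cut-off.
5. Label the cut-offs exploratory pending external validation.

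The cost is a short addition to the SAP and a little more code, with no extra patients or measurements. Data collection is planned to run to August 2026, so the change can be made before analysis. The downside is that the reported accuracy will look less favourable.
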